## **17.0 APPENDICES**

#### Appendix A Responsibilities of the Investigator

- 1. Conduct the appropriate study in accordance with the protocol and GCP considering the rights, safety and wellbeing of human subjects.
- 2. When a part of the important activities related to the study are delegated to a sub-investigator or the study collaborator, prepare the lists of activities to be delegated and responsible personnel, submit the lists to the head of the investigational site in advance to get them accepted.
- 3. Prepare a written informed consent form and other written information, and update as appropriate.
- 4. Confirm the contents of the clinical study agreement.
- 5. Provide necessary information on the protocol, medications and responsibilities of individual personnel to the sub-investigator and study collaborator, and provide guidance and supervision.
- 6. Screen subjects who meet the requirements of the protocol, provide the explanation of the study in writing and obtain the written consent.
- 7. Assume responsibility for all the medical judgement related to the study.
- 8. Ensure in collaboration with the head of the investigational site that sufficient medical care for all clinically significant AEs related to the study are provided to subjects throughout and beyond the period when subjects participate in the study, upon obtaining consent from the subject.
- 9. If a subject consults other medical institution or other department, notify the physician of the medical institution or department of the subject's participation in the study, as well as the end and termination of the study in writing, and document such records.
- 10. In case of urgent report of a SAE, immediately notify the head of the investigational site and the Sponsor in writing.
- 11. Determine the need of emergency key code blinding of a subject in case of emergency.
- 12. Prepare correct and complete eCRFs, and submit them to the Sponsor with electronic signature.
- 13. Check and confirm the contents of eCRFs prepared by the sub-investigator or transcribed from the source data by the study collaborator, and submit them to the Sponsor with electronic signature.
- 14. Discuss any proposal from the Sponsor including update of the protocol.
- 15. Notify the head of the investigational site of the end of the study in writing.

## Appendix B Pregnancy and Contraception

## **Contraception and Pregnancy Avoidance Procedure**

## Male Subjects and Their Female Partners

From the signing of informed consent, throughout the duration of the study, and for 12 weeks (84 days) after last dose of study drug, any nonsterilized\*\* male subjects who are sexually active with a female partner of childbearing potential\* must use adequate contraception. In addition, they must be advised not to donate sperm during this period. Females of childbearing potential who are partners of male subjects are also advised to use additional contraception as shown in the table on containing adequate contraception below.

\* Females NOT of childbearing potential are defined as those who have been surgically sterilized (hysterectomy, bilateral oophorectomy or tubal ligation), or who are postmenopausal (eg, defined as at least 2 years since last regular menses with an FSH of >40 IU/L).

\*\* Sterilized males should be at least 1 year post-bilateral vasectomy and have confirmed that they have obtained documented absence of sperm in the ejaculate, or have had a bilateral orchidectomy.

Barrier methods (each time the subject has intercourse)	Intrauterine devices (IUDs)	Hormonal contraceptives
Male condom with spermicide.	Copper T PLUS condom.	Combined pill.
	Progesterone T PLUS condom.	

An acceptable method of contraception is defined as one that has no higher than a 1% failure rate.

Subjects will be provided with information on acceptable methods of contraception for 12 weeks (84 days) after last dose of study drug, as part of their informed consent process, and will be asked to sign a consent form stating that they understand the requirements for avoidance of pregnancy in partners and of sperm donations for 12 weeks (84 days) after their last dose of study drug.

## Pregnancy

If any pregnancies in the partner of a male subject, during the study or for 12 weeks (84 days) after the last dose, should be recorded following authorization from the subject's partner.

If the pregnancy in the partner of a male subject occurs during or after administration of blinded drug, the investigator or sub-investigator must inform the subject of his right to receive treatment information. If the subject chooses to receive unblinded treatment information, that individual's blind should be broken by the investigator or sub-investigator. Any subjects randomized to placebo need not be followed.

If the female partner of a male subject agrees to have her primary care physician informed, the investigator or sub-investigator should notify the primary care physician that her partner was participating in a clinical study at the time she became pregnant and provide details on the study drug that the subject has received (blinded or unblinded, as applicable).

TAK-906	
Study ID TAK-906-1004	Page 68 of 71
Protocol	6 June 2017

All pregnancies in the female partners of male subjects will be followed to final outcome, using the pregnancy form, with the consent of the female partners of those male subjects. The outcome, including any premature termination, must be reported to the Sponsor. An evaluation after any birth of a child will also be conducted.

Variables	Timing of	procedures (standard)	Acceptable window	
Examinations only for diagnostic screening (a)	Screening period	Days -28 to -2	Not applicable	
Physical examination	Screening period	Days -28 to -2	Not applicable	
	Check-in	Day -1	Not applicable	
	Treatment period	Day 1: Predose.	From awakening to immediately	
		Day 5: Before morning dose.	prior to (morning) dose	
		Days 2 and 8: 24 hours postdose of Days 1 and 7, respectively.	Within ±1 hour	
	Follow-up	Day 14	Within ±2 days	
Weight	Screening period	Days -28 to -2	Not applicable	
	Check-in	Day -1	Not applicable	
	Treatment period	Day 7: Predose.	From awakening to immediately prior to dose	
	Follow-up	Day 14	Within ±2 days	
Vital signs	Screening period	Days -28 to -2	Not applicable	
	Check-in	Day -1	Not applicable	
	Treatment period	Days 1 and 7: Predose.	From awakening to immediately	
		Days 3 to 6: Before morning dose.	prior to (morning) dose	
		Days 1 and 7: 1, 2, 4, and 6 hours postdose.	Within ±30 minutes	
		Days 2 and 8: 24 hours postdose of Days 1 and 7, respectively.	Within ±1 hour	
	Follow-up	Day 14	Within ±2 days	
12-lead ECG	Screening period	Days -28 to -2	Not applicable	
	Check-in	Day -1	Not applicable	
	Treatment period	Days 1 and 7: Predose.	From awakening to immediately	
		Day 5: Predose.	prior to (morning) dose	
		Days 1 and 7: 1, 2, 4, and 6 hours postdose.	Within ±30 minutes	
		Days 2 and 8:24 hours postdose of Days 1 and 7, respectively.	Within ±1 hour	
		Day 5: 1 and 2 hours postdose.	Within ± 30 minutes	

# Appendix C Acceptable Time Window for Study Procedure

#### TAK-906 Study ID TAK-906-1004 Protocol

Variables	Timing of	procedures (standard)	Acceptable window
Hematology and chemistry	Screening period	Days -28 to -2	Not applicable
for safety assessments (b)	Check-in	Day -1	Not applicable
	Treatment period	Days 2 and 8: 24 hours postdose of Days 1 and 7, respectively.	Within ±1 hour
		Day 5: Before morning dose.	From awakening to immediately prior to morning dose
	Follow-up	Day 14	Within ±2 days
Urinalysis for safety	Screening period	Days -28 to -2	Not applicable
assessments	Check-in	Day -1	Not applicable
	Treatment period	Days 2 and 8: 24 hours postdose of Days 1 and 7, respectively.	From awakening to 1 hour post-scheduled time
		Day 5: Before morning dose.	From awakening to immediately prior to morning dose
	Follow-up	Day 14	Within ±2 days
Plasma sample for TAK-906 PK	Treatment period	Day 1: Predose.	From awakening to immediately prior to dose
		Day 1: 0.5, 1, 1.5, 2, 3, 4, 6, 8, 12, and 16 hours postdose.	Within ±5 minutes
		Day 2: 24 hours postdose of Day 1.	Within ±15 minutes
		Days 3 to 6: Just before morning dose.	From 15 minutes predose to immediately prior to morning dose
		Day 7: Predose.	Immediately prior to dose
		Day 7: 0.5, 1, 1.5, 2, 3, 4, 6, 8, 12, and 16 hours postdose.	Within ±5 minutes
		Day 8: 24 hours postdose of Day 7.	Within ±15 minutes
Urine sample for TAK-906 PK	Treatment period	Day 1: Predose (spot).	From awakening to immediately prior to dose
		Days 1 to 2: 0-6, 6-12, and 12-24 hours postdose.	Not applicable
		Day 7: 0-6 and 6-12 hours postdose.	Not applicable

Footnotes are on the following page.

Variables	Timing of	procedures (standard)	Acceptable window	
Serum sample for PD (prolactin)	Treatment period	Day 1: Predose.	From awakening to immediately prior to dose	
		Day 1: 1, 2, 4, and 6 hours postdose.	Within ±5 minutes	
		Day 2: 24 hours postdose of Day 1.	Within ±15 minutes	
		Days 3 to 6: Just before morning dose.	From 15 minutes predose to immediately prior to morning dose	
		Day 7: Predose.	Immediately prior to dose	
		Day 7: 1, 2, 4, and 6 hours postdose	Within ±5 minutes	
		Day 8: 24 hours postdose of Day 7.	Within ±15 minutes	
	Follow-up	Day 14	Within ±2 days	

BMI=body mass index, ECG=electrocardiogram\_HBsAg=henatitis B virus surface antigen\_HCV=hepatitis C virus, HIV=human immunodeficiency virus,

PK=pharmacokinetics, PD=pharmacodynamics.

(a) Including height measurement, BMI calculation, immunological test (HBsAg, anti-HCV, HIV antibody/antigen, and syphilis screen), prolactin assessment for safety, urine drug screen, urine cotinine test, and alcohol screen (urine alcohol test/alcohol breath test).

(b) Serum prolactin level will be measured at Screening for safety assessment.

Total blood s	sampling volumes	for an individua	l subject is shown below:
1000000		101 411 11141 114 400	

Sample Type	Sample	1					Total
	Volume (mL)	Screening	Day -1	Days 1-2	Days 3-8	Follow-up	Volume (mL)
Hematology	2	1	1	1	2	1	12
Chemistry	5	1 (a)	1	1	2	1	30
Blood for TAK-906 PK	4	0	0	12	16	0	112
Blood for PD	5	0	0	6	10	1	85

PK=pharmacokinetics, PD=pharmacodynamics,

HBsAg=hepatitis B virus surface antigen, HCV=hepatitis C virus, HIV=human immunodeficiency virus.

(a) One 5-mL sample collected for blood chemistry test at Screening will be also used for immunological test (HBsAg, anti-HCV, HIV antibody/antigen, and syphilis screen), and prolactin assessment for safety.

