# 5.0 TRIAL OBJECTIVES AND ENDPOINTS

# 5.1 Hypothesis

This study was designated based on the following hypotheses:

- TAK-906 will be safe and well tolerated in Japanese healthy male subjects in the doses to be tested.
- Following the first dose, one or more well-tolerated doses of TAK-906 will result in a 3-fold increase in serum prolactin at the maximum level of serum prolactin (Cmax) as compared to baseline for each treatment period (single dose period, multiple dose period).

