## 11.1.4 PD Analysis

For the serum prolactin concentration, the observed values and their changes from baseline will be summarized by dose over each scheduled sampling time using descriptive statistics.

A more detailed analysis will be presented in the SAP.

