7.0 METHODS OF ANALYSIS AND PRESENTATION

7.1 General Principles

7.1.1 Study Definitions

The following definitions and calculation formulas will be used.

- TEAE: An AE whose date of onset occurs on or after the start of study drug. A TEAE whose relationship to study drug is missing will be considered drug-related. A TEAE whose intensity is missing will be considered severe.
- PTE: An AE whose date of onset occurs before the start of study drug..
- Descriptive statistics: number of subjects with non-missing values, mean, standard deviation, maximum, minimum, and quartiles, including geo-mean, geo-CV as needed
- QTcF interval (msec): QT interval (msec) / (RR interval (msec)/1000)^{0.33} (rounded to the nearest whole number)
- Baseline values: The last evaluable observation (ie, non-missing) before the first dose of study drug. If no evaluable observation is obtained before the first dose, the baseline value will be missing.
- TEAE occurred in single dose period: A TEAE occurred prior to start of multiple dosing.
- TEAE occurred in multiple dose period: A TEAE occurred from Day 3 postdose through Day 14 (follow-up visit).

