7.9.2 Pharmacodynamic Analysis

7.9.2.1 Serum Concentrations of prolactin level

Analysis Set:	PD Analysis Set
Analysis Variables :	Serum concentration of prolactin
Visit:	Day 1: Predose, 1, 2, 4, 6, and 24 hours post single dose.
	Days 3-6: Just before morning dose.
	Day 7: Predose, 1, 2, 4, 6, and 24 hours post morning dose.
	Day 14
Analytical Methods:	The following summaries will be provided by dose.
	(1) Summary of Serum Concentrations by Time Point

Descriptive statistics for observed values and change from Day 1predose will be provided for each time point. In addition, geometric mean, geometric standard deviations, and %CV will be provided

- (2) Concentration-time Profiles for Individual Subjects Observed values will be plotted using individual case plot.
- (3) Mean Concentration-time Profiles with Standard Deviations Mean of serum concentration will be plotted by time point using linear scale for Days 1-7, Day 1 and Day 7 respectively.
- (4) Geometric Mean Concentration-time Profiles with Geometric Standard Deviations Geometric Mean of serum concentration will be plotted by time point using natural log scale for Days 1-7, Day 1 and Day 7 respectively.

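### The Day 1 predose prolactin sample, the only reference for PD change, has a looser window than the later predose samples, so its timing may differ from theirs and between subjects

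*Protocol*

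**What the plan says.** Protocol Appendix C sets three predose windows for serum prolactin:

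- Day 1: "From awakening to immediately prior to dose".
- Days 3 to 6: "From 15 minutes predose to immediately prior to morning dose".
- Day 7: "immediately prior to dose", with no earlier limit offered.

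Post-dose samples on Days 1 and 7 are allowed ±5 minutes at 1 to 6 hours and ±15 minutes at 24 hours.

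For the analysis, SAP 7.9.2.1 states: "Descriptive statistics for observed values and change from Day 1predose will be provided for each time point". This agrees with the general baseline rule in SAP 7.1.1, "The last evaluable observation (ie, non-missing) before the first dose of study drug", and with the change-from-baseline summary in Protocol 11.1.4. The Day 1 predose draw is the only PD sample before treatment. The Screening prolactin is a local-laboratory safety test, and no Day -1, replicate or time-matched PD baseline is planned.

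Protocol 5.1 expects a 3-fold rise in maximum prolactin "as compared to baseline for each treatment period". The SAP defines no separate baseline for the multiple dose period.

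**The concern.** One measurement per subject is the reference for all of that subject's prolactin changes. It is also the one scheduled sample during confinement whose window is not tied closely to dosing. Any error in it passes unchanged into every change value for that subject, and nothing averages it out.

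The prolactin windows for Day 1 predose, Days 3 to 6 and Day 7 predose match the TAK-906 plasma rows of the same appendix. For drug concentration a wide Day 1 window does no harm: no dose has been given, and exclusion criterion 2 bars earlier recipients of TAK-906. Prolactin differs because it is a hormone already present before dosing and under dopamine control (Protocol 6.3.3.3). If its level moves between awakening and dosing, the time of the draw matters.

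At stake are the change-from-baseline summaries for the only PD endpoint, in groups of 6 active subjects, and any comparison of the results with the 3-fold hypothesis.

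**Working it through.** The plan states no figure to reproduce, and Protocol 11.3 says the sample size is not power-based. The check is a comparison of text followed by simple arithmetic.

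**1. Windows compared (Appendix C, serum PD)**

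| Sample | Earliest permitted draw | Latest permitted draw |
|---|---|---|
| Day 1 predose (the reference) | awakening | just before dose |
| Days 3 to 6 | 15 minutes before dose | just before dose |
| Day 7 predose | just before dose | just before dose |

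The windows overlap at their late end. A site may draw the Day 1 sample just before dosing but is not required to.

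**2. Width of the Day 1 window**

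Width = dosing time − awakening time. The documents give no awakening time; 05:00 to 07:00 is assumed. Dosing is at 07:00 to 08:00 in footnote (d) of the Schedule of Study Procedures and at 08:00 to 09:00 in Table 7.b, so 07:00 to 09:00 covers both.

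- Narrowest: 07:00 − 07:00 = 0 minutes.
- Awakening at 06:00: 60 to 180 minutes.
- Widest: 09:00 − 05:00 = 240 minutes, which is 240/15 = 16 times the Days 3 to 6 window.

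**3. Effect on the planned statistic**

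Let B be the value that a just-before-dose draw would give, and fB the value actually drawn on Day 1. The documents do not give f. The SAP plans differences, so each of the subject's changes is off by −(f − 1)B, the same amount at every time point. This error cancels when two of the same subject's changes are compared with each other. It does not cancel in the change from baseline itself. If f varies between subjects, it adds spread.

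**4. Illustration on the ratio scale of the hypothesis**

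Observed fold = 3/f when the true fold is 3. Apparent change at a later predose sample with no drug effect = 1/f − 1.

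| Assumed f | Observed fold | Apparent predose change |
|---|---|---|
| 0.8 | 3.75 | +25% |
| 1.0 | 3.00 | 0% |
| 1.1 | 2.73 | −9% |
| 1.25 | 2.40 | −20% |
| 1.5 | 2.00 | −33% |

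**5. What is not affected**

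Observed post-dose concentrations and Cmax (SAP 7.9.2.1 and 7.9.2.2) are not baseline-subtracted. AUC uses the predose value only as its first point. Under a trapezoidal rule (assumed), the AUC error is 0.5 × 1 h × (f − 1)B. At f = 1.5 this is 0.25B, against 24B for a flat 24-hour profile at level B: 0.25/24, about 1%.

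**The case against.** A reader might infer that the Day 1 baseline will be too high, so that the plan understates the prolactin rise and makes prolactin appear to fall with repeated dosing. The documents do not support that. They say only that dopamine inhibits prolactin and that D2 blockade raises it; they say nothing about how prolactin behaves after waking. Both direction and size therefore remain open. Nor do the documents show that the baseline *will* be taken under different conditions. The windows overlap, subjects are confined, the 10-hour fast is the same on every dosing morning, and Protocol 6.3.4 asks that procedures be kept close to schedule.

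Other points also limit the concern:

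- Placebo subjects have the same window and are not excluded from the PD summaries, so a systematic shift should appear in them too. The protection is partial: 3 × 2 = 6 placebo subjects are planned, with no formal comparison.
- The SAP plans no fold-change analysis. It plans accumulation ratios for PK but none for prolactin.
- Actual sampling times are recorded (Protocol 9.3), so the spread can be described, although the SAP plans no adjustment for it.
- A dose-related window would standardise the draw relative to dosing, not relative to waking. It would still leave one baseline unmatched in clock time to the 1 to 6 hour samples.

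These points stand, and they lower the priority. They do not explain why the reference sample should have the loosest predose window, and the documents offer no PD reason for it.

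**Conclusion.** The concern holds in a limited form. Day 1 predose prolactin may be drawn at any time from awakening to dosing, the later predose samples are tied to the dose, and the Day 1 value is the sole reference for change. If prolactin varies over that interval, the change summaries and any reading of the 3-fold hypothesis carry avoidable error that may differ between subjects.

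The size cannot be derived from the documents. The fold and percentage figures rest on assumed values of f, and the window widths on an assumed awakening time. This is a cheap improvement of minor priority to a descriptive secondary endpoint. It does not show that the PD results would be biased in a known direction.

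**What to change.** In Protocol Appendix C, change the Day 1 predose window for serum PD (prolactin) to run from 15 minutes before the dose until just before it, as on Days 3 to 6. Leave the plasma and urine PK windows unchanged. The change must be in place before the first subject is dosed, because a baseline cannot be collected again.

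The cost is one table cell and somewhat less slack on the morning of Day 1. That morning also carries the final eligibility check, physical examination, vital signs, ECG, spot urine and PK blood, so it is busier than the mornings on which the short window already applies. The change still looks feasible in confined subjects.

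Separately, the morning dosing times in footnote (d) of the Schedule of Study Procedures and in Table 7.b disagree and must be reconciled, since a dose-related window takes its clock time from them.

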3.0 LIST OF ABBREVIATIONS

AE	adverse event
ALT	alanine aminotransferase
AST	aspartate aminotransferase
AUC	area under the plasma concentration-time curve
BCRP	breast cancer resistance protein
BID	twice daily
BMI	body mass index
C _{max}	maximum observed plasma concentration
CNS	central nervous system
CRO	contract research organization
СҮР	cytchrome P-450
DA	dopamine
CCI	
eCRF	electronic case report form
ECG	electrocardiogram
EPS	extrapyramidal symptoms
FDA	Food and Drug Administration
FIH	first-in-human
FSH	follicle stimulating hormone
GCP	Good Clinical Practice
GE	gastric emptying
GGT	gamma-glutamyl transferase
GI	gastrointestinal
GP	gastroparesis
HBsAg	hepatitis B virus surface antigen
HCV	hepatitis C virus
HDPE	high density poleythylene
hERG	human ether-a-go-go related gene
HIV	human immunodeficiency virus
ICH	International Conference on Harminsation
INR	international normalized ratio
IRB	institutional review board
IUD	intrauterine device
LFT	liver function test
LLC	limited liability company
LOEL	lowest observed effect level
MAD	multiple-ascending dose

МСН	mean corpuscular hemoglobin		
МСНС	mean corpuscular hemoglobin concentration		
MCV	mean corpuscular volume		
MedDRA	Medical Dictionary for Regulatory Activities		
MHW	Ministry of Health and Welfare		
NOAEL	no-observed-adverse-effect level		
OAT	organic anion transporter		
OATP	organic anion transporting polypeptide		
ОСТ	organic cation transporter		
ОТС	over-the-counter		
PD	pharmacodynamics		
РК	pharmacokinetics		
P-gp	P-glycoprotain		
CCI			
RBC	red blood cell		
SAD	single-ascending dose		
SAE	Serious adverse event		
SAP	statistical analysis plan		
SD	standard deviation		
SUSARs	suspected unexpected serious adverse reactions		
TEAE	treatment-emergent adverse event		
tmax	maximum concentration time		
ULN	upper limit of normal		
US	United States		
USP	United States Pharmacopoeia		
WBC	white blood cell		

4.0 **OBJECTIVES**

4.1 **Primary Objectives**

The primary objective of the study is to evaluate safety and tolerability of single and multiple oral doses of TAK-906 in Japanese healthy male subjects.

4.2 Secondary Objectives

The secondary objective of the study is to evaluate PK and PD of single and multiple oral doses of TAK-906 in Japanese healthy male subjects.

4.3 Additional Objectives

4.4 Study Design

4.4.1 Trial Design

This is a phase 1, randomized, double-blind, placebo-controlled, single and multiple dose, parallel-group study in up to 3 cohorts of Japanese healthy male subjects, to assess the safety, tolerability, PK, and PD of TAK-906.

Each cohort will consist of 8 subjects where 6 subjects will be randomized to receive TAK-906 and 2 subjects will be randomized to receive matching placebo. The study population will be 24 Japanese healthy male subjects. The randomized subjects will receive a single dose of blinded study drug on Day 1 followed by multiple doses of blinded study drug BID for 5 days from Day 3 to Day 7, except that an evening dose of study drug will not be administered on Day 7. If a subject discontinues from the trial, a replacement subject may be enrolled, if deemed appropriate by the investigator and Sponsor. The investigational site should contact the Sponsor for the replacement subject's medication identification number.

In Cohorts 1 and 2, subjects will be randomized to receive TAK-906 maleate 50 mg, 100 mg, or matching placebo. In Cohort 3, subjects will be randomized to receive TAK-906 maleate 10 mg, or matching placebo. For each cohort, follow-up assessments will occur on Day 14 which is 7 days

TAK-906-1004	Page 9 of 33
Statistical Analysis Plan	10 Nov 2017

after completion of the last treatment dose. Dose escalation to Cohort 2 will be based on a full blinded review of safety and tolerability data until follow-up assessments from Cohort 1. Cohort 3 will be conducted in parallel with Cohort 1 or 2. Dose level in Cohort 2 may be changed within the range up to 100 mg, as appropriate, based on safety and pharmacokinetic data in preceding cohorts, ie, 50 mg BID in Cohort 1 or 10 mg BID in Cohort 3 (if applicable) of this study; however, no higher dose than the proposed highest dose (100 mg BID).

(IRB) approval to revise the study protocol.

The planned dose levels of TAK-906 to be evaluated are outlined in Table 1.

Cohort (a)	TAK-906 malesate Dose (a, b, c)		Subjects
Conort (a)	Single Dose Period	Multiple Dose Period (d)	Subjects
1	50 mg single dose	50 mg BID for 5 days	6 TAK-906
	on Day 1	from Days 3 to 7	2 Placebo
2	100 mg single dose	100 mg BID for 5 days	6 TAK-906
	on Day 1	from Days 3 to 7	2 Placebo
3	10 mg single dose	10 mg BID for 5 days	6 TAK-906
	on Day 1	from Days 3 to 7	2 Placebo

Table 1Summary of Dose Cohorts

BID=twice daily

(a) Dose escalation to Cohort 2 will be based on a full blinded review of safety and tolerability data until follow-up assessments from Cohort 1. Cohort 3 will be conducted in parallel with Cohort 1 or 2.

- (b) A single dose and all morning doses of trial medication in multiple dose periods will be administered after fast of at least 10 hours that continues for at least 4 hours after dosing with restricted water intake for at least 1 hour prior to and after dosing. The evening dose will be administered 12 hours after the morning dose and at least 2 hours after dinner.
- (c) Dose level in Cohort 2 may be changed within the range up to 100 mg, as appropriate, based on safety and pharmacokinetic data in preceding cohorts, ie, 50 mg BID in Cohort 1 or 10 mg BID in Cohort 3 (if applicable) of this study
- (d) An evening dose of study drug will not be administered on Day 7.

